#### 1.2 **Purpose**

The purpose of this study is to explore the efficacy and safety of LTP001 in participants with WHO Group 1 pulmonary hypertension (PH), also referred to as Pulmonary Arterial Hypertension (PAH).

This proof of concept study will be executed as the efficacy of SMURF1 inhibition has not yet been established in the PAH population. This study will provide insights to whether SMURF1 inhibition is effective in reducing the pulmonary vascular resistance, improves patient symptom burden and increases the time to clinical worsening. These endpoints are considered relevant for the characterization of the disease progression in PAH. **CCI** 

# Amended Protocol Version v03 (Clean)

# Objectives, endpoints and estimands 2

Table 2-1 Objectives and related endpoints				
Objective(s)		Endpoint(s)		
Primary objective(s)		En	dpoint(s) for primary objective(s)	
•	To assess the efficacy of LTP001 in participants with pulmonary arterial hypertension (PAH).	•	Change from baseline right heart catheterization PVR at Week 25	
Sec	condary objective(s)	Endpoint(s) for secondary objective(s)		
•	To evaluate the effect of LTP001 on Six Minute Walk Distance (6MWD)	•	Change from baseline in 6MWD at Weeks 13 and 25	
•	To evaluate the effect of LTP001 on hemodynamic parameters other than PVR	•	Right heart catheterization assessments including RV pressures, pulmonary artery pressures, wedge pressure, and cardiac output at Week 25	
•	To assess the effect of LTP001 on measurements of right ventricular function		Change from baseline in tricuspid annular plane systolic excursion (TAPSE) by echocardiography at Weeks 5, 13, and 25	
			Change from baseline in tricuspid annular systolic velocity (TASV) by echocardiography at Weeks 5, 13, and 25	
			Change from baseline of peak velocity of excursion (RV S') by echocardiography at Weeks 5, 13, and 25 Change from baseline in fractional area change (FAC) by echocardiography at Weeks 5, 13, and 25	
•	To assess the impact of LTP001 on patient reported outcomes (PRO)	•	Change from baseline in EmPHasis-10 and PAH- SYMPACT at Weeks 13 and 25	
•	To assess the safety and tolerability of LTP001.	•	AEs, SAEs, vital signs, ECGs, safety laboratory measurements	
•	To assess the impact of LTP001	•	Time to any of the following:	
	on Time to Clinical Worsening (TTCW).		Death	
			
 
Hospital stay (≥ 24 h) due to worsening of PAH. Worsening of PAH is defined by the following right heart failure related signs and symptoms: syncope or near syncope, cyanosis, increase of breathlessness, clinically relevant deterioration of exercise capacity, decrease of oxygen saturation, increased peripheral edema, hepatomegaly, and ascites
 
	
			
 
Worsening of PAH resulting in need for lung transplantation or balloon atrial septostomy
 
	
			
 
Initiation of parenteral prostanoid therapy, chronic oxygen therapy, or any other PAH-specific therapies or need for increase of diuretics for more than 4 weeks due to worsening of PAH
 
	

Objective(s)	Endpoint(s)	
	
 
Disease progression (switch in modified New York Heart Association/WHO FC by at least one grade).
 
	
	
 
Significant drop in 6MWD (15% from baseline or more) due to PAH-worsening
 
	
To investigate the pharmacokinetics (PK) of LTP001	
 
Cmax and tmax (Day 1 and Week 25)
 
	
To assess the impact of LTP001 on the N-terminal fragment of the prohormone B-type natriuetic pentide (NT-proBNP)	
 
N-terminal fragment of the prohormone B-type natriuetic peptide
 
	

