**Novartis** 

minimize burden on participants, and offer them increased flexibility to participate in the study from an off-site location. This has the potential to

broaden access to clinical trials for both participants and investigators. The hybrid approach will allow participants to maintain contact with investigator, both in-person during clinic visits and through the telemedicine platform during off-site participation

4.1.1

The background therapy will be the previously used therapy by the participant. PAH-directed maintenance therapy needs to be tolerated and kept stable for 6 weeks prior to the RHC and 6MWT assessments preceding randomization, but diuretic therapy may be adjusted if needed (for details please refer to Section 6.2.1). Otherwise, the background therapy should not be changed during the study. If there is a deterioration of the participant's PAH condition requiring an escalation of concomitant PAH-specific treatment the participant should be discontinued from the study treatment (for detailed study discontinuation criteria see Section 9.1) and subsequently return for the End of Treatment assessments.

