## 6.2.3 Rescue medication

Rescue medication is defined as an additional medication, or change in the dose of an existing medication.

A clinical worsening of PAH requiring a change in dose of an existing PAH-specific medication, or the addition of a new PAH specific medication, may fulfill criteria for discontinuation for study treatment (see Section 9.1.1). PAH-specific medications include: all ERAs, PDE5i, sGC stimulators and oral, intravenous or subcutaneous prostacyclin analogues and receptors agonists. For allowed modifications of PAH directed therapies and adjustments of diuretic therapy please refer to Section 6.2.1.

Use of rescue medications must be recorded on the Concomitant medications/Significant non-drug therapies eCRF after signing the informed consent.

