- The PAH-SYMPACT questionnaire (Mccollister, et al., 2016) (Chin, et al., 2018) consists of 11 symptom items across two domains (cardiopulmonary and cardiovascular symptoms) and 11 impact items across two domains (physical and cognitive/emotional impacts). Symptom items and one item about the use of oxygen are assessed daily for one week; impact items are assessed on the last day of the week. Each item is scored on a five-point scale (0-4) except for the item of using oxygen (scale 0-1). The total PAH-SYMPACT score will be calculated as the sum of impact item scores and mean weekly symptom item scores. For each symptom item, its mean weekly score will be calculated as the average daily item score taken within the 7-day interval.

NT-proBNP

The N-terminal fragment of the prohormone B-type natriuetic peptide (NT-ProBNP) is reflective of right ventricular distress. Measurements collected at baseline and at visits on Week 13, and 25 will be used for analysis.

Time to clinical worsening (TTCW)

TTCW will be defined as time to any of the following events:

Death

- Hospital stay (≥ 24 h) due to worsening of PAH.
- Worsening of PAH resulting in need for lung transplantation or balloon atrial septostomy
- Initiation of parenteral prostanoid therapy, chronic oxygen therapy, or any other PAHspecific therapies or need for increase of diuretics for more than 4 weeks due to worsening of PAH
- Significant drop in 6MWD (15% from baseline or more) due to PAH-worsening

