2.6.2 Statistical hypothesis, model, and method of analysis

6MWT

Change from baseline in walked distance for 6MWT at visits will be analyzed based on mixed model repeated measures, adjusting for effects of treatment, visit as categorical factors and treatment*visit and baseline*visit interactions. Model based estimates of the mean effect will be reported for each treatment group along with the treatment difference, the 2-sided 80% confidence interval for treatment difference, and one-sided p-value

TTCW

Time to clinical worsening will be analyzed using survival models (i.e., Kaplan-Meier, cox regression) if adequate number of events occur during the study to characterize the survival curve. Participants without the event will be considered as censored at the end of the time at risk. The hazard ratio and the corresponding 80% confidence intervals will be computed using the appropriate method. If there is no adequate number of events, the number (and percentage) of participants with clinical worsening will be summarized by treatment and overall.

Echocardiography

Descriptive statistics (N, mean, SD, CV% mean, geometric mean, CV% geometric mean, median, min, and max) summarizing echocardiography parameters and their changes from baseline will be summarized by visit for treatment group and overall.

Panels of individual spaghetti plots over time/visit for each echocardiography parameter will be provided.

All echocardiography parameters will be listed by participant, and visit and if ranges are available, abnormalities will be flagged.

PROs

For emPHasis-10, total score and change from baseline of total score will be summarized by visit for treatment and overall. For PAH-SYMPACT, the total score and change from baseline will be summarized by visit for treatment and overall.

NT-proBNP

NT-proBNP (visits on week 13 and 25) will be analyzed based on mixed model repeated measures, adjusting for the baseline, treatment groups, visit and treatment-by-visit interaction. Model based estimates of the mean effect will be reported for each treatment group along with

the treatment difference, the 2-sided 80% confidence interval for treatment difference, and onesided p-value. Depending on the distribution of NT-proBNP data, the analysis for NT-proBNP might be through logarithms to reduce outliers and skewness.

RHC

RHC parameters and their change from baseline will be summarized by visit for treatment group and overall.

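### The TTCW therapy component counts starting a PAH drug but not raising the dose of an existing one for worsening, so a participant escalated in this way who meets no other component is censored as event-free

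*Protocol*

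**What the plan says.** **Endpoint.** Protocol Table 2-1 defines TTCW as the time to the first of several events. The therapy component is "Initiation of parenteral prostanoid therapy, chronic oxygen therapy, or any other PAH-specific therapies or need for increase of diuretics for more than 4 weeks", attributed to worsening PAH. SAP 2.6.1, the operative definition for the analysis, repeats it: "Initiation of parenteral prostanoid therapy, chronic oxygen therapy, or any other PAHspecific therapies or need for increase of diuretics for more than 4 weeks". The other components are death, a PAH-related hospital stay of at least 24 h, need for lung transplantation or septostomy, "Significant drop in 6MWD (15% from baseline or more) due to PAH-worsening", and, in Table 2-1 and SAP 1.2 only, "Disease progression (switch in modified New York Heart Association/WHO FC by at least one grade"). SAP 2.6.1 leaves out the functional-class component, although SAP section 4 reports no change from the protocol.

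**Dose escalation elsewhere in the protocol.** Section 6.2.3 describes "A clinical worsening of PAH requiring a change in dose of an existing PAH-specific medication" and names the addition of a new PAH drug as a separate case; either may meet the criteria for stopping study treatment. Section 4.1.1 says of a deterioration "requiring an escalation of concomitant PAH-specific treatment the participant should be discontinued from the study treatment". Section 6.2.2 says that a change in PAH therapy required by worsening should lead to stopping treatment.

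**Analysis.** SAP 2.6.2 states: "Participants without the event will be considered as censored at the end of the time at risk". The end of the time at risk is not defined. Kaplan-Meier and Cox methods, with an 80% interval for the hazard ratio, are used only if there are enough events; otherwise participants with worsening are counted by arm.

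**The concern.** Within one component, the plan counts an increase for diuretics but only a start for PAH drugs. Since 6.2.3 separates a dose change from a new drug, a dose increase cannot fairly be read as a start. Inclusion criterion 9 means that everyone enters on at least one PAH drug, so raising a current drug is a natural response to worsening.

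A participant handled this way can leave study treatment because PAH worsened and still enter the TTCW analysis as a non-event. Such censoring is linked to the outcome it is meant to be independent of. The fallback count of participants with worsening has the same gap.

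TTCW is also reported at the interim analysis (SAP 2.13). The offer of the open-label extension depends on there being no excess of clinical worsening over placebo (Protocol 6.1.4), although that section does not say that TTCW is the measure.

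**Working it through.** The documents give no TTCW event count, hazard ratio or power, so there is no planned figure to reproduce. The check is a comparison of texts, followed by an illustration on assumed inputs.

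**1. Does a dose increase of an existing PAH drug count?**
- Protocol Table 2-1, SAP 1.2 and SAP 2.6.1: starting parenteral prostanoid, chronic oxygen or other PAH-specific therapy counts, as does a diuretic increase of more than 4 weeks. A PAH-drug dose increase is not named.
- Protocol 6.2.3: dose change and new drug are listed as two different things.
- Result: it is not an event in itself.

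**2. What happens to study treatment?** The statements differ.
- 4.1.1: on escalation for deterioration, study treatment *should* be stopped.
- 6.2.2: a change required by worsening *should* result in stopping.
- 6.2.3: a dose change *may* fulfil the stopping criteria.
- 9.1.1: stopping is required for *additional* PAH therapy beyond the scope of 6.2.1; a dose increase is not named.
- 4.5, procedural risks: a participant needing a change in PAH therapy because of progression is discontinued from the *study*.
- 6.2.1.1: doses should stay unchanged, but IV prostacyclin may change by up to 20%.

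**3. Can another component catch the same participant?** Yes, but not reliably.
- Walk distance: Protocol section 3 schedules the test at Weeks 5, 13 and 25, and calls for end-of-treatment procedures as soon as possible after early stopping. That test may follow the escalation and be improved by it.
- Functional class: in Table 2-1 and SAP 1.2, but absent from SAP 2.6.1.
- Death, hospital stay, transplant or septostomy need, and sustained diuretic increase: each requires its own occurrence.
- Later events: under 9.1.1, discontinued participants are followed and new treatments and adverse events are recorded. Whether a later event counts depends on the undefined time at risk.

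**4. Weight of one participant.** 44 randomized 3:1 gives 44 × 3/4 = 33 on LTP001 and 44 × 1/4 = 11 on placebo. One event is 1/11 = 9.1% of placebo or 1/33 = 3.0% of LTP001.

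**5. Illustration (event risks and shares are assumptions).** Take true event risks of 18% on LTP001 and 36% on placebo: 33 × 0.18 = 5.9 and 11 × 0.36 = 4.0 events. Assuming exponential times, HR = ln(1 − p_LTP001) / ln(1 − p_placebo) = ln(0.82)/ln(0.64) = 0.44. Let a share of each arm's events be dose increases only, and hence uncounted, and multiply each p by (1 − share):

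| Uncounted, placebo | Uncounted, LTP001 | Calculation | HR |
|---|---|---|---|
| 0% | 0% | ln(0.82)/ln(0.64) | 0.44 |
| 25% | 25% | ln(0.865)/ln(0.73) | 0.46 |
| 50% | 25% | ln(0.865)/ln(0.82) | 0.73 |
| 50% | 0% | ln(0.82)/ln(0.82) | 1.00 |
| 25% | 50% | ln(0.91)/ln(0.73) | 0.30 |

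Equal loss barely moves the hazard ratio. Unequal loss moves it a good deal, in either direction.

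**6. Precision.** The 80% interval multiplies and divides the HR by exp(1.2816 / √(d × 0.75 × 0.25)) for d events: 2.55 at d = 10, 2.85 at 8, 3.35 at 6 and 4.39 at 4. Lost events also widen an already wide interval.

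**The case against.** The strongest defence is that restricting the component to new therapy is a legitimate choice. It keeps investigator-driven dose titration out of the composite, and the other components are there to catch real worsening. SAP 2.6.2 censors only participants with no component at all, and deterioration serious enough to prompt escalation may well show in walk distance, functional class or a hospital stay. Discontinuation reasons and concomitant medications are reported by arm, so these cases would stay visible.

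Much of this stands, and it rules out several stronger readings that a reader might infer:
- *That every escalated participant must stop treatment.* The wording runs from *should* to *may*, and 9.1.1 speaks of additional therapy.
- *That every escalated participant is censored as event-free.* This holds only if no other component is met.
- *That 6.2.3 contradicts the endpoint.* It describes worsening that leads to a dose change and does not define TTCW.
- *That counting diuretic increases is itself inconsistent.* A permitted adjustment can also be an outcome event when it is sustained and due to worsening.

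What does not stand is the idea that the other components close the gap. The walk test is infrequent and may come after the escalation, and the SAP's operative list lacks functional class. A listing of discontinuation reasons does not enter the hazard ratio or the fallback count. Nor does the argument about investigator-driven events separate the two cases, since starting a new therapy is equally the investigator's decision.

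**Conclusion.** The gap is real and appears in both documents: a dose increase of an existing PAH drug for worsening is not a TTCW event, although the protocol treats such escalation as a reason that should, or may, end study treatment. A participant with no other component is censored, and that censoring is plausibly informative.

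The effect cannot be sized from the documents. They do not say how many participants would be escalated without meeting another component, or whether everyone's current drug could be raised. The only firm figure is the weight of one participant: 9.1% of placebo or 3.0% of LTP001. A reader might infer that the hazard ratio is pulled towards 1 if LTP001 works. That is not supported: under the assumed risks it ranged from 0.30 to 1.00 around a true 0.44, depending on how the uncounted share differs between arms.

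Nor does the point reach the trial's main conclusion. TTCW is secondary, is modelled only if events are adequate and carries no power claim. The primary PVR analysis, the sample size and the PVR futility rule are unaffected. It is a worthwhile and cheap correction to a secondary endpoint.

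**What to change.** In Protocol Table 2-1, SAP 1.2 and SAP 2.6.1, reword the PAH-drug part of the component to: *initiation of, or increase in dose of existing, PAH-specific therapy beyond the changes allowed in 6.2.1.1, due to worsening of PAH*. Keep the oxygen and diuretic parts. Date the event at the day of the change and derive it from the concomitant medication eCRF together with the discontinuation reason.

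At the same time, align the component list in SAP 2.6.1 with Table 2-1 and define the end of the time at risk, including for participants who have stopped study treatment. The sponsor must also reconcile the differing discontinuation statements in Protocol 4.1.1, 4.5, 6.2.2, 6.2.3 and 9.1.1; this review takes no position on which should prevail.

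**Cost.** Wording in two documents and one programmed derivation. Sections 6.2.1 and 6.2.3 already require these treatments to be recorded, so no new data collection is needed, and the endpoint change alters no treatment rule. The downside is one more investigator-driven event type in the composite.

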# 2.1 Primary estimands

Not applicable.

# 2.2 Secondary estimands

Not applicable.

# 3 Study design

This is a randomized, participant- and investigator-blinded, placebo-controlled, parallel group study of LTP001 or placebo on top of standard of care in participants with PAH.

Standard of care includes one or more of the following treatments: prostacyclin analogues or receptor agonists (if I.V., dose adjustments must be within 20% of initial stable dose), endothelin receptor antagonists, phosphodiesterase type 5 inhibitors, and soluble guanylate cyclase stimulators.

Figure 3-1 Study Design

A screening period of 8 weeks will be used to assess eligibility prior to randomization. Screening procedures can occur throughout the 8 week screening period, except for those procedures which are defined at specific time-points such as the right heart catheterization, qualifying 6MWT, PROs, and CCI

in the Assessment Schedule (Table 8-1). In particular, the screening period may be used to assess if a participant appears to be adequately stable on current therapy and that the criteria for allowed concomitant medication is adhered to for the time period defined in Section 6.2.1 and Section 5.1 prior to pre-dose qualifying 6MWD and the baseline right heart catheterization. Participants who fulfill all enrollment criteria earlier may have a shorter screening period.

Preference is for screening procedures to occur from least invasive to most invasive (echocardiography, right heart catheterization). Since laboratory measurements require central review, laboratory assessments should occur 15 or more business days prior to planned randomization. The right heart catheterization and the qualifying 6 minute walk test prior to first dose should occur within 20 days prior to randomization/planned first dose. Note, the RHC and qualifying 6MWT may be performed on the first dosing day if they are completed prior to randomization. During screening, participants will be given guidance on how to use the wearable device (if they have chosen to use it), which will be provided approximately 7 days prior to scheduled start of dosing. On Day 1, eligible participants will be randomized to one of two treatment arms. Approximately 44 participants with PAH will be randomized in a 3:1 ratio to either oral LTP001 or placebo daily for 24 weeks.

During the treatment period, visits will occur approximately every 4 weeks for assessments of efficacy and safety as per the assessment schedule (see Table 8-1). Safety assessments will include physical examinations, ECGs, vital signs, standard clinical laboratory evaluations (hematology, blood chemistry, and urinalysis), and adverse event and serious adverse event monitoring. Right heart catheterization to measure PVR for the primary objective and primary efficacy endpoint is performed at the end of the treatment period on Day 169 (Week 25). Other measures of efficacy include echocardiography (Week 5, Week 13, and Week 25) and the 6MWT (Week 5, Week 13, and Week 25). PAH-SYMPACT and emPHasis-10 will be collected for 7 day intervals with the seventh day of collection occurring within the allotted visit window for the following visits: Day 1, Week 5, Week 9, Week 13, Week 17, Week 21, and Week 25.

Following the end of the treatment period, participants will have one follow-up visit approximately 30 days after end of treatment (Week 29), which will serve as the End of Study (EOS) visit. All visits from Week 5 to Week 25 have a plus 5 day visit window and Week 29 has a plus or minus 5 day visit window. If treatment is ended early for any reason, the end of treatment visit procedures should occur as soon as possible thereafter.

An unblinded interim analysis (IA) is planned for when approximately 20 participants complete the 24-week treatment period, and may include analyses to assess sample size, efficacy, PK, PD, or safety. The analysis may be used for internal decision making of the further development of LTP001 in PAH patients. Further analyses will be prepared for review by the DMC per the DMC charter.

Pending the safety and efficacy profile of LTP001 that is observed in the current study (absence of study treatment discontinuation criteria or study stopping rules or an emerging safety concern in the review of the data), participation in the open label extension study may be offered to participants once the extension study is approved by the competent authorities and review boards.

Transition from the current study in an open label extension (OLE) study will be defined in the separate protocol. For participants enrolling into the OLE study, the EOS visit will be skipped in order to continue treatment in the OLE protocol. Replacement of such procedures done at the EOS will be defined in the OLE study protocol.

